#### 7.2 PARTICIPANT DISCONTINUATION/WITHDRAWAL FROM THE STUDY

Participants have the option to withdraw from study participation at any time.

An investigator may discontinue a participant from the study for the following reasons:

- Any event or medical condition or situation occurs such that continued collection of follow-up study data would not be in the best interest of the participant.
- The participant meets an exclusion criterion (either newly developed or not previously recognized) that precludes further study participation.

The reason for participant discontinuation or withdrawal from the study will be recorded for acceptability/feasibility tracking purposes.

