condition). Participants in the Pilot MRT will complete daily 1-minute (5-item) assessments of their mood, social relationships, emotional awareness, interest in activities, and efficacy to cope with stress. All participants will receive a brief, weekly 10-minute 'Sunday survey' assessing various aspects of their health and well-being. Pilot MRT participants will be randomized each week at a 2:1 ratio to receive (or not receive) a Monday personalized feedback report that provides a graphical depiction summary of their scores up until that point in time on depression, anxiety, perceived stress, and flourishing scales, with a written description of the corresponding severity levels and links to available mental health resources. Pilot MRT participants will also be randomized each week, at a 2:1 ratio, to receive or not receive supportive text messages offering strategies and tips for health promotion and stress management during the week, which includes a daily-level 50:50 randomization (during weeks when randomized to receive texts). At the end of six weeks, all participants will complete a 25-minute follow-up assessment, with additional items for those in the Pilot MRT condition assessing feasibility/acceptability of the PF reports and text-message intervention components.

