#### 5.2 EXCLUSION CRITERIA

Exclusion criteria will include: (1) being under the age of 17, (2) currently be receiving mental health therapy/counseling from a healthcare professional, (3) experiencing minimal depressive symptoms (PHQ-9 < 5), (4) experiencing moderately severe to severe depressive symptoms (PHQ-9 >14).

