#### 7.3 LOST TO FOLLOW-UP

A participant will be considered lost to follow-up if they do not complete the six-week follow-up assessment.

Before a participant is deemed lost to follow-up, study staff will make up to two telephone contacts and up to two e-mail contacts following the initial survey invitation.

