### 8 STUDY ASSESSMENTS AND PROCEDURES

## 8.1 ENDPOINT AND OTHER NON-SAFETY ASSESSMENTS

To recruit participants, we will obtain e-mail addresses of 2,500 first-year undergraduate students from the registrar (2,000 randomly selected from UM-Ann Arbor, and 500 from UM-Flint, which reflects the full annual enrollment of first-year undergraduate students at the UM-Flint campus) and invite them to participate in an 8-minute survey screen of their mental health, with an online consent form. We anticipate approximately 425 students will consent to participate and complete the **screening survey**, and that 142 students will meet criteria for a positive screen of mild-moderate depressive symptoms (PHQ-9 score of 5-14) and no current psychotherapy for the intervention portion of the study. We anticipate that 85% of the 142 participants who screened eligible for the study will continue to this next phase of the study, provide a cell-phone numbers, and complete the **baseline survey** (all within the same Qualtrics flow of the screening survey). The screening survey will be administered to all invited participants who consent to participate and takes approximately 8 minutes to complete. It will be sent out on a Tuesday, with reminders on Friday, and following Monday. Participants are deemed eligible if they score 5-14 on the PHQ-9, denoting mild-to-moderate depressive symptoms **and** report they are not currently enrolled in a form of mental health care (e.g., therapy). The baseline survey will be administered to participants screening positive on the screen, when they provide their cell phone number, and takes 10-15 additional minutes to complete. Randomization (3:1 to intervention versus assessment-only) occurs after baseline survey has been completed. Daily surveys will be administered to participants in the intervention group only, and take approximately 1 minute to complete, with links to the survey texted at 8pm each day. Weekly surveys are administered to all participants on Sunday evenings and take approximately ten minutes to complete. The final follow-up survey takes approximately 25 minutes to complete and will be administered to all randomized participants (n=120) on their sixth Sunday of the project. Administration of all surveys will be conducted via an online, automated system (Qualtrics).

[figure not shown]

Figure 1. Enrollment Flowchart

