*Sleep (Baseline/Weekly-abbv./Follow-up).* We will use a 9-item adapted version of the Pittsburgh Sleep Quality Index (Buysse et al., 1989) to capture self-report of sleep duration, quality, and sleeping difficulties at baseline and follow-up. Two items focused on sleep duration and quality will be utilized at weekly assessments.

*Physical activity (Baseline/Weekly/Follow-up).* We use three derived from the Youth Behavior Risk Survey (Grunbaum et al., 2002) to assess frequency and duration of moderate and vigorous exercise at baseline, weekly, and follow-up assessments.

*Interpersonal functioning (Baseline/Follow-up).* We use 15 items from the Interpersonal Needs Questionnaire (Van Orden et al., 2012), a self-report measure of perceived burdensomeness and thwarted belongingness-- two interpersonal constructs believed to contribute to suicidal desire.

*Emotional Awareness (Baseline/Weekly/Follow-up).* We use the 6-item subscale 'Emotional Awareness' from the Difficulties in Emotion Regulation Scale (Gratz & Roemer, 2004) at baseline, weekly, and follow-up assessments.

*Coping Behaviors (Baseline/Follow-up).* We use the 28-item Brief Cope (Carver, 1997) to assess frequency of using 14 specific coping behaviors that encompass various forms of problem-focused coping, emotion-focused coping, and avoidant coping strategies.

*Suicidal thoughts and behaviors (Baseline/Weekly—abbv./Follow-up—abbv.).* 4 items adapted from the National comorbidity survey will assess history of suicidal thoughts and behaviors at baseline, and two items will assess past-week suicidal thoughts at weekly and follow-up assessments.

*Readiness for help-seeking (Baseline/Weekly-abbv./Follow-up).* We use four items on a 10-point readiness scale (King et al., 2022) for seeking help from different sources (e.g., family/friends, online resources, professional services, support group) for mental health at baseline and follow-up. Weekly assessments will include two items: readiness for online resources and professional services.

*Intervention Acceptability (Follow-up).* We use a modified version of the 4-item Acceptability of Intervention Measure (Weiner et al., 2017) to obtain self-report subjective ratings of intervention acceptability and participants will indicate acceptability of numerous intervention features (e.g., frequency/timing of surveys, personalized feedback; confidentiality; satisfaction; helpfulness) using a 7-point agreement scale (strongly disagree to strongly agree).

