#### 9.4.2 ANALYSIS OF THE PRIMARY ENDPOINT(S)

The primary outcomes include feasibility and acceptability measured by: (1) percentage of eligible participants who agree to participate, (2) percentage of completed follow-ups, (3) number of and reasons for withdrawals, (4) of those randomized to text-messages, percentage of participants who remain active (i.e. do not request to stop messages), (5) visits/clicks for an individual's personalized feedback report page, and (6) participant self-reported satisfaction with the intervention components.

---

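### Section 7.2 lets an investigator end participation for a newly developed exclusion criterion, which after randomisation can only be a measured outcome; use is likely rare and the cost per use is small

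*Combined protocol and SAP*

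**What the plan says.** Section 7.2 introduces its two grounds with "An investigator may discontinue a participant from the study for the following reasons". The first is participant welfare. The second is "The participant meets an exclusion criterion (either newly developed or not previously recognized) that precludes further study participation". The rule is discretionary, and it ends participation in the study, not only in the intervention.

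Section 5.2 lists four exclusion criteria. Two are age under 17 and current therapy or counselling. The other two read "3) experiencing minimal depressive symptoms (PHQ-9 < 5), (4) experiencing moderately severe to severe depressive symptoms (PHQ-9 >14".

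On follow-up, Section 8.1 says the final survey "will be administered to all randomized participants (n=120) on their sixth Sunday of the project", and Section 7.3 says "A participant will be considered lost to follow-up if they do not complete the six-week follow-up assessment". Section 9.4.2 lists "2) percentage of completed follow-ups" among the primary outcomes, along with the number of withdrawals and the reasons for them. Acceptability is also primary. Its self-report scale is given only at week 6 ("to obtain self-report subjective ratings of intervention acceptability", Section 8.1), in a survey that comes "with additional items for those in the Pilot MRT condition assessing feasibility/acceptability of the PF reports and text-message intervention components" (Section 4.1).

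**The concern.** The second bullet has two limbs. Ineligibility at entry that comes to light later is a normal ground for removal and is not questioned here. The newly developed limb is different. Screening and baseline are one survey flow and randomisation follows, so a criterion that develops newly does so after randomisation. By then it describes how the student is doing under the assigned condition: improved, worsened, or now in treatment.

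The clause therefore permits removal that depends on an outcome. A removed student counts as lost to follow-up under Section 7.3, so a primary feasibility percentage falls because of an investigator's action and not the student's. The student's week-6 answers are not collected. A student who worsens is also one whose view of the feedback reports and messages matters for the adaptive version the study is meant to inform.

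**Working it through.** **1. What can newly develop.**

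| Criterion (5.2) | Can it arise after randomisation? | Where the trial measures it |
|---|---|---|
| Age under 17 | No | Not applicable |
| Current therapy | Yes | Service use at week 6 (1.3, 8.1) |
| PHQ-9 below 5 | Yes (improvement) | Weekly and week 6 (1.3); secondary objective (3) |
| PHQ-9 above 14 | Yes (worsening) | Weekly and week 6 (1.3); secondary objective (3) |

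Section 1.3 lists both the PHQ-9 and service use under outcome evaluations. The newly developed limb has no use that is not an outcome.

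**2. What the rest of the protocol assumes.** The feedback reports carry wording for PHQ-9 bands from 0-4 up to 20-27 (6.1.1). Worsening depressive symptoms are an expected adverse event (8.3.1) and are foreseen during the study (10.1.6). The week-6 survey asks about therapy in the past six weeks (8.1). Each of these presupposes that students who leave the 5-14 range or start therapy remain in the study.

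**3. How the clause could come into use.** Participants are told that responses are not monitored or reviewed (2.3.3, 8.2), and no section sets an eligibility re-check. Two openings remain: adverse events noticed during review of assessments or reported by e-mail (8.3.4), and the weekly quality review of data files (10.1.8). A PHQ-9 below 5 is not an adverse event. Surveys ask about therapy only at screening and week 6, too late to cost a week-6 survey. In practice this leaves mainly PHQ-9 above 14.

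**4. The denominator, reproduced.** 2,500 × 17% = 425; 142/425 = 33.4% (stated as 33%); 142 × 85% = 120.7 (stated as 120). A 3:1 split of 120 gives 90 and 30.

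**5. Cost per use before week 6,** if the student would otherwise have completed:

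- overall: 1/120 = 0.83 percentage points
- intervention arm: 1/90 = 1.11 points, and one of at most 90 sets of acceptability ratings
- assessment-only arm: 1/30 = 3.33 points

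Removal after weekly survey *w* loses 6 − *w* of the six post-baseline assessments: five after week 1, one after week 5. In the intervention arm that is 5/540 = 0.93% down to 1/540 = 0.19% of the 540 weekly outcomes in Section 9.4.1.

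The documents give no completion rate. If it were 90% without the clause (assumed; 108/120), then 1, 3 and 6 uses among would-be completers give 107/120 = 89.2%, 105/120 = 87.5% and 102/120 = 85.0%.

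**6. The exploratory PHQ-9 contrast, by illustration only.** The documents give no standard deviations, effect size or rate of use. A simulation assumed mean PHQ-9 8, between-person SD 3-4.5, weekly SD 1.5-3, entry scores 5-14, and a 2-point benefit reached by week 3. Removal was applied to a share of students with any PHQ-9 above 14 in weeks 1-5.

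| Assumed share removed | Removed of 120 | Points of completion |
|---|---|---|
| 10% | 0.3-2.2 | 0.3-1.9 |
| 25% | 0.8-5.6 | 0.7-4.7 |

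The week-6 arm difference at 25% use was:

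- full data: −1.94 to −2.00
- completers only: −1.86 to −1.95
- imputed by arm from screening and weekly scores: −1.94 to −2.00
- imputed from the screening score without arm: −1.78 to −1.96

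With no true effect, no arm difference appeared beyond simulation error (about 0.01).

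**The case against.** The best case for leaving the text alone is that the bullet covers only a criterion that precludes further participation. No section says that a PHQ-9 outside 5-14 or a start of therapy does so, and the rest of the protocol keeps such students in. On that reading the limb has little to act on. The answer is that no section says which newly met criterion does preclude participation. Either the limb does nothing, and removing it is free, or it acts on outcomes.

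Several other objections stand, at least in part:

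- **Reach.** The rule is discretionary, procedures are automated and responses are not monitored. Use should be rare.
- **Transparency.** Section 7.2 records the reason for discontinuation, and reasons for withdrawal are themselves a primary outcome, so removals could be separated out afterwards. No feasibility threshold is stated, so no decision rule turns on 0.8 points. Separating removals out does not, however, recover answers that were never collected.
- **Overlap.** A student who worsens could still be removed under the welfare bullet. The gain is confined to removals that welfare does not justify.
- **Missing data.** Section 9.4.1 plans multiple imputation, which can largely protect the PHQ-9 contrast if the model includes arm and weekly scores. The section does not specify the model. Imputation does not restore an observed completion percentage. Helpfulness ratings of messages already received (6.1.1) would remain in any case.

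A reader might also infer that the clause contradicts the intent-to-treat approach in Section 9.3. It does not. That section governs analysis, and a removed student stays in the randomised set; the loss is in data collection.

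**Conclusion.** The point holds as a minor flaw in the wording of Section 7.2. As written, the clause allows removal on a post-randomisation outcome, which sits badly with Sections 6.1.1, 8.1, 8.3.1 and 10.1.6. The conclusion about the wording and the per-use costs follow from the documents alone. Those costs are maxima, because the student might not have completed anyway.

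How often the clause would be used is unknown. The 10% and 25% shares, the standard deviations and the 2-point benefit are assumptions, and the simulated data model is simple and linear. They support only the statement that the PHQ-9 contrast moves little at limited use.

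A reader might go further and infer that everyone who leaves the 5-14 range must be removed, or that the arm comparison is materially biased. The documents do not support either inference. The rule is permissive, no section prescribes a re-check, and the study is a descriptive pilot with no formal hypotheses (9.1).

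**What to change.** In Section 7.2, limit the second bullet to ineligibility that existed at entry and was not recognised then. Add one sentence: a later PHQ-9 outside 5-14, or a start of therapy, is recorded as an outcome and is not by itself a reason to stop surveys. Keep the participant-welfare bullet. Section 9.3 needs no change.

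The cost is a small text edit, with no extra data, staff or participants. The investigator gives up one discretionary ground for removal, and the welfare bullet covers the cases where removal would be justified. Section 7.1 already lets participants drop texts or reports while continuing surveys. With the change, the loss attributable to this limb is 0 of 120.

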#### 7.3 LOST TO FOLLOW-UP

A participant will be considered lost to follow-up if they do not complete the six-week follow-up assessment.

Before a participant is deemed lost to follow-up, study staff will make up to two telephone contacts and up to two e-mail contacts following the initial survey invitation.

### 8 STUDY ASSESSMENTS AND PROCEDURES

## 8.1 ENDPOINT AND OTHER NON-SAFETY ASSESSMENTS

To recruit participants, we will obtain e-mail addresses of 2,500 first-year undergraduate students from the registrar (2,000 randomly selected from UM-Ann Arbor, and 500 from UM-Flint, which reflects the full annual enrollment of first-year undergraduate students at the UM-Flint campus) and invite them to participate in an 8-minute survey screen of their mental health, with an online consent form. We anticipate approximately 425 students will consent to participate and complete the **screening survey**, and that 142 students will meet criteria for a positive screen of mild-moderate depressive symptoms (PHQ-9 score of 5-14) and no current psychotherapy for the intervention portion of the study. We anticipate that 85% of the 142 participants who screened eligible for the study will continue to this next phase of the study, provide a cell-phone numbers, and complete the **baseline survey** (all within the same Qualtrics flow of the screening survey). The screening survey will be administered to all invited participants who consent to participate and takes approximately 8 minutes to complete. It will be sent out on a Tuesday, with reminders on Friday, and following Monday. Participants are deemed eligible if they score 5-14 on the PHQ-9, denoting mild-to-moderate depressive symptoms **and** report they are not currently enrolled in a form of mental health care (e.g., therapy). The baseline survey will be administered to participants screening positive on the screen, when they provide their cell phone number, and takes 10-15 additional minutes to complete. Randomization (3:1 to intervention versus assessment-only) occurs after baseline survey has been completed. Daily surveys will be administered to participants in the intervention group only, and take approximately 1 minute to complete, with links to the survey texted at 8pm each day. Weekly surveys are administered to all participants on Sunday evenings and take approximately ten minutes to complete. The final follow-up survey takes approximately 25 minutes to complete and will be administered to all randomized participants (n=120) on their sixth Sunday of the project. Administration of all surveys will be conducted via an online, automated system (Qualtrics).

[figure not shown]

Figure 1. Enrollment Flowchart

**Primary Outcomes:** The primary outcomes include feasibility and acceptability measured by: (1) percentage of eligible participants who agree to participate, (2) percentage of completed follow-ups, (3) number of and reasons for withdrawals, (4) of those randomized to text-messages, percentage of participants who remain active (i.e. do not request to stop messages), (5) visits/clicks for an individual's

personalized feedback report page, and (6) participant self-reported satisfaction with the intervention components. Participants' feedback will be obtained with Likert scale items and open-ended questions, including overall perspective on personalized feedback reports, and receiving text messages, experience (e.g., ease of accessing intervention components, acceptability of intervention timing, frequency, and duration), and recommended changes.

### **Additional measures**

*Daily Survey:* The daily survey contains five items that assess: 1) mood (On a scale from 1 (lowest/worst) to 10 (highest/best), how was your mood today? \_\_\_\_), 2) connectedness (My social relationships were supportive and rewarding today (Likert Strongly Disagree (1) to Strongly Agree (7))), 3) coping efficacy (I feel confident that I can cope with the demands and/or stressors in my life (Likert Strongly Disagree (1) to Strongly Agree (7))), 4) Emotional awareness (I was aware of my emotional state and feelings today (Likert Strongly Disagree (1) to Strongly Agree (7))), 5) Interest/energy (I was engaged and interested in my activities today (Likert Strongly Disagree (1) to Strongly Agree (7))).

#### Screen/Baseline/Weekly/Follow-up Measures

*Flourishing (Screen/Weekly/Follow-up).* The Flourishing Scale (Diener et al., 2010) is a brief 8-item summary measure of the respondent's self-perceived success in important areas such as relationships, self-esteem, purpose, and optimism. The scale provides a single psychological well-being score (range: 8-56).

*Depression (Screen/Weekly/Follow-up).* The PHQ-9 (Kroenke et al., 2002) is a 9-item standardized self-report scale for the assessment of depressive symptoms, with a scale range of 0-27.

*Anxiety (Screen/Weekly/Follow-up).* The GAD-7 (Spitzer et al., 2006) is a 7-item validated self-report scale for the assessment of symptoms consistent with generalized anxiety disorder, with a scale range of 0-21.

*Coping self-efficacy (Screen/Weekly-abbv./Follow-up).* We use a thirteen-item coping self-efficacy scale (Chesney et al., 2006) to assess confidence in engaging in specific coping strategies when under stress at baseline and follow-up. During weekly assessments, an item from each of the scale's three factors (problem solving, seeking support, stopping unpleasant thoughts/emotions) will be administered.

*Loneliness (Screen/Weekly/Follow-up).* The UCLA Loneliness scale (Russel et al., 1978) is a self-report measure assessing quality of interpersonal connections and relationships-- we will utilize the 3-item short form for baseline, weekly, and follow-up assessments, which has a scale range of 0-6.

*Perceived Stress (Screen/Weekly-abbv./Follow-up).* We use the 10-item Perceived Stress Scale (Cohen et al., 1983) at baseline and follow-up assessment; the 4-item PSS short form is used at weekly assessments.

*Mental health service utilization (Screen/Follow-up).* At baseline, participants will be assessed for lifetime and current use of therapy/counseling from a professional health provider (those currently receiving services are excluded from the trial). At follow-up, participants are asked about any (and number of sessions) counseling or therapy sessions for emotional/mental health in the past six weeks.

*Trauma history (Baseline).* The Life Event Checklist (LEC-5; Weathers et al., 2013) will ask participants to indicate whether they have experienced one of twelve types of Criterion A traumatic events, and if so, whether or not these had been experienced in the past 12 months.

*Sleep (Baseline/Weekly-abbv./Follow-up).* We will use a 9-item adapted version of the Pittsburgh Sleep Quality Index (Buysse et al., 1989) to capture self-report of sleep duration, quality, and sleeping difficulties at baseline and follow-up. Two items focused on sleep duration and quality will be utilized at weekly assessments.

*Physical activity (Baseline/Weekly/Follow-up).* We use three derived from the Youth Behavior Risk Survey (Grunbaum et al., 2002) to assess frequency and duration of moderate and vigorous exercise at baseline, weekly, and follow-up assessments.

*Interpersonal functioning (Baseline/Follow-up).* We use 15 items from the Interpersonal Needs Questionnaire (Van Orden et al., 2012), a self-report measure of perceived burdensomeness and thwarted belongingness-- two interpersonal constructs believed to contribute to suicidal desire.

*Emotional Awareness (Baseline/Weekly/Follow-up).* We use the 6-item subscale 'Emotional Awareness' from the Difficulties in Emotion Regulation Scale (Gratz & Roemer, 2004) at baseline, weekly, and follow-up assessments.

*Coping Behaviors (Baseline/Follow-up).* We use the 28-item Brief Cope (Carver, 1997) to assess frequency of using 14 specific coping behaviors that encompass various forms of problem-focused coping, emotion-focused coping, and avoidant coping strategies.

*Suicidal thoughts and behaviors (Baseline/Weekly—abbv./Follow-up—abbv.).* 4 items adapted from the National comorbidity survey will assess history of suicidal thoughts and behaviors at baseline, and two items will assess past-week suicidal thoughts at weekly and follow-up assessments.

*Readiness for help-seeking (Baseline/Weekly-abbv./Follow-up).* We use four items on a 10-point readiness scale (King et al., 2022) for seeking help from different sources (e.g., family/friends, online resources, professional services, support group) for mental health at baseline and follow-up. Weekly assessments will include two items: readiness for online resources and professional services.

*Intervention Acceptability (Follow-up).* We use a modified version of the 4-item Acceptability of Intervention Measure (Weiner et al., 2017) to obtain self-report subjective ratings of intervention acceptability and participants will indicate acceptability of numerous intervention features (e.g., frequency/timing of surveys, personalized feedback; confidentiality; satisfaction; helpfulness) using a 7-point agreement scale (strongly disagree to strongly agree).

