### 1.2 SCHEMA

### 1.3 SCHEDULE OF ACTIVITIES

	Screening	Baseline Survey	Weekly (Every Sunday for 5 weeks)	Daily (42 days; Intervention-only)	6-week follow-up (6 th Sunday)
Informed Consent	X				
Demographics	X				
Primary Randomization (Survey Only)		X			
Secondary Randomization (MRT)		X			
Outcome Evaluations					
Flourishing Scale	X		X	*	X
Depression (PHQ-9) and Anxiety (GAD-7)	X		X		X
Coping Self-Efficacy	X		*		X
UCLA-Loneliness Scale	X		X		X
Mental Health Service Utilization	X				X
Pittsburgh Sleep Quality Index-Adapted		X	*		X
Physical Activity (YRBS Adaptation)		X	*		X
Interpersonal Needs Questionnaire (INQ)		X			X
DERS-Emotional Awareness		X	X	*	X
Brief COPE		X			X
National Comorbidity Survey (Suicidal Ideation and Behavior)		X	*		*
Perceived Stress Scale		X	*	*	X
Life Events Checklist (LEC-5)		X			
Readiness for Help-Seeking		X	*		X
Daily Mood				*	
Feasibility/Acceptability Survey					X
Adverse Events Reporting		X			X
Note: X = Full-scale; * = Abbreviated version					

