## 8.2 SAFETY ASSESSMENTS

There will be no direct contact between participants and study staff, as consent and assessment procedures are completed digitally. Individuals who are deemed ineligible due to elevated depressive symptoms are presented with mental health resources and crisis contacts when exiting the survey platform. Likewise, individuals indicating recent thoughts of suicide are presented with resources and crisis contact information and are informed that study staff do not review their responses.

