### 8.3.2 DEFINITION OF SERIOUS ADVERSE EVENTS

Serious adverse event (SAE) is an adverse event that: results in death; is life-threatening (places the participant at immediate risk of death from the event as it occurred); results in inpatient hospitalization or prolongation of existing hospitalization; results in a persistent or significant disability/incapacity; results in a congenital anomaly/birth defect; or based upon appropriate medical judgment, may jeopardize the subject's health and may require medical or surgical intervention to prevent one of the other outcomes listed in this definition.

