### 8.3.4 TIME PERIOD AND FREQUENCY FOR EVENT ASSESSMENT AND FOLLOW-UP

The occurrence of an adverse event (AE) or serious adverse event (SAE) may come to the attention of study personnel during review of assessments of a study participant or if a participant makes direct contact with study staff through the project e-mail address. All AEs, not otherwise precluded per the protocol, will be captured on the appropriate case report form (CRF). Information to be collected includes event description, time of onset, assessment of severity, relationship to study procedures, and time of resolution/stabilization of the event. All AEs occurring while on study will be documented appropriately regardless of relationship. Within 48 business hours of learning of these events, the coordinator will then bring all possible AEs to the attention of the PI for evaluation and appropriate reporting. AE's will be assessed by the PI for expectedness (expected, unexpected) and relatedness (definitely related, probably related possibly related, unlikely related, not related). A log of all AE's will be maintained by the study coordinator, and the log will be additionally reviewed for completeness at weekly intervals during the active recruitment period.

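### After baseline, no described item asks about suicidal behaviour or psychiatric admission, so such an event during the six weeks can go uncounted

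*Combined protocol and SAP*

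**What the plan says.** Section 8.1 (measures list) states that "4 items adapted from the National comorbidity survey will assess history of suicidal thoughts and behaviors at baseline". For every later survey it states that "two items will assess past-week suicidal thoughts at weekly and follow-up assessments". The schedule in Section 1.3 carries the instrument under its full name, "National Comorbidity Survey (Suicidal Ideation and Behavior", and marks the weekly and follow-up versions as abbreviated.

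On service use, Section 8.1 says: "At follow-up, participants are asked about any (and number of sessions) counseling or therapy sessions for emotional/mental health in the past six weeks". Admissions and emergency visits are not mentioned.

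On safety events, the definition of a serious adverse event in Section 8.3.2 includes one that "results in inpatient hospitalization or prolongation of existing hospitalization". Section 1.3 has a row for "Adverse Events Reporting", marked at baseline and at the 6-week follow-up. Section 8.3.4 says events "may come to the attention of study personnel during review of assessments of a study participant or if a participant makes direct contact with study" personnel by e-mail. Section 8.2 says: "There will be no direct contact between participants and study staff". Section 2.3.3 adds that participants are told their answers are not monitored, and Section 8.2 that those reporting recent suicidal thoughts are told staff do not review their answers.

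**The concern.** The trial enrols students with PHQ-9 scores of 5 to 14. It names onset of suicidal ideation as an expected adverse event (Section 8.3.1) and uses suicide attempt history as a baseline descriptor (Section 9.4.5). The same construct is not followed up: the plan records whether a student has ever made an attempt, but describes no question on whether one happened during the study.

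Two things follow. First, the safety record of the pilot, which Section 2.3.2 says will inform a later randomized trial, could show no attempts because no described item asked. Second, the reporting time limit in Section 8.3.6 for study-related life-threatening events runs from the point at which the study learns of the event, so an event that is never learned of starts no clock.

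**Working it through.** The documents state no figure on this point, so there is none to reproduce. The check is to go through everything described after baseline and ask whether it would elicit a suicide attempt or a psychiatric admission.

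| Post-baseline source | Section | Content as described |
|---|---|---|
| Suicide items, weekly and follow-up | 8.1 | Two items, thoughts in the past week |
| Daily survey (intervention arm only) | 8.1 | Five items: mood, connectedness, coping efficacy, emotional awareness, interest |
| Depression, anxiety, flourishing, loneliness, stress, coping self-efficacy, sleep, activity, emotional awareness, readiness for help | 8.1 | None described as asking about attempts or admission |
| Interpersonal Needs Questionnaire and Brief COPE, follow-up | 8.1 | Burdensomeness and belongingness; coping behaviours |
| Service use, follow-up | 8.1 | Counselling or therapy sessions in six weeks |
| Acceptability, follow-up | 8.1 | Ratings and open comments on the intervention |
| Adverse event reporting, follow-up | 1.3 | Not described |

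The number of described items on suicidal behaviour is therefore zero at each of the 5 + 1 = 6 assessments after baseline.

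The remaining routes are passive:

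- Review of assessments (8.3.4). Review cannot find what no item asks.
- A participant's e-mail to the project (8.3.4).
- The recorded reason for discontinuation or withdrawal (7.2).
- Up to two telephone and two e-mail contacts before a participant is classed as lost to follow-up (7.3). No safety question is described for them.

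For scale, let p be the probability that a participant makes an attempt within six weeks. The documents give no value, so p is an assumption shown over a range. With n = 120 (Section 9.2), the expected number is 120p and the chance of at least one is 1 − (1 − p)^120.

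| Assumed p | Expected number | Chance of at least one |
|---|---|---|
| 0.1% | 0.12 | 11% |
| 0.25% | 0.30 | 26% |
| 0.5% | 0.60 | 45% |
| 1% | 1.20 | 70% |

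If every participant were asked and none reported an attempt, the exact one-sided 95% upper bound on the risk would be 1 − 0.05^(1/n): 2.5% for all 120, 3.3% for the 90 in the intervention arm and 9.5% for the 30 in the assessment-only arm. Without a question, a count of zero does not support even these bounds.

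**The case against.** The strongest reply is that the scheduled adverse event report at six weeks may already ask. Section 8.1 is titled as covering non-safety assessments, so an adverse event form would not be expected there, and the case report form and Manual of Procedures are not part of the documents. This stands to the extent that one cannot say an attempt will be missed. A reader might infer that the study would learn of an event only if the student wrote in; the six-week entry and the routes in Sections 7.2, 7.3 and 8.3.4 do not support that. But Section 8.2, where a safety question would be expected, describes none, and the case report form in Section 8.3.4 is where staff record an event once known, not a question put to the participant.

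A reader might also infer that the schedule contradicts Section 8.1 because its row label includes behaviour. It does not: the row names the full instrument, the asterisk marks an abbreviated version, and Section 8.1 says what the abbreviation contains.

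A third tempting reading is that a planned safety conclusion is undermined. None is planned: safety analyses are N/A (9.4.4), events of special interest are N/A (8.3.8) and there are no formal hypotheses (9.1). The bounds above show that 120 participants could not support a strong conclusion in any case. The loss is in ascertainment and in what is handed to the next trial.

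Lastly, acting on individual positive answers is not free, because participants are told their answers are not monitored or reviewed. That stands and shapes the fix.

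**Conclusion.** The concern holds in this form: as described, suicidal behaviour is asked about at baseline and at none of the six later assessments, and no described item asks about psychiatric admission. A suicide attempt or admission on study can therefore go uncounted unless the undescribed six-week adverse event report or a passive route brings it to light. The feasibility and acceptability outcomes are unaffected.

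The finding about the items rests on the text alone. The 11% to 70% chance of at least one attempt rests on the assumed range for p; it indicates scale and does not estimate missed events. That a suicide attempt is an especially important serious event here is a judgement, reasonable given Sections 8.3.1, 8.3.2 and 9.4.5, but not one the protocol states.

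Separately, Section 8.3.4 relies on review of assessments, while Sections 2.3.3 and 8.2 say answers are not monitored or reviewed. The distinction may be between real-time monitoring and later review, but the documents do not draw it.

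**What to change.** - At the 6-week follow-up, repeat the suicidal-behaviour item(s) already used at baseline, reworded to cover the time since enrolment.
- Add hospital or emergency visits for mental health to the existing past-six-week service-use question.
- State what the six-week adverse event entry asks. If it already covers attempts and admissions since enrolment, describing it closes most of the gap.
- Report the counts descriptively by arm, each with the number of participants who answered, so that a zero can be read against its denominator.
- Reconcile Section 8.3.4 with Sections 2.3.3 and 8.2 on whether and when staff look at responses. How positive answers are handled is for the sponsor and the IRB to decide.

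The cost is two or three more sensitive items, of a kind participants already answered at baseline, in a survey of about 25 minutes, plus a small protocol and IRB change. The wording given to participants may also need to change, depending on how the sections are reconciled. The new items will not reach those who do not complete the follow-up, which is why the number answering must be shown.
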